7.6.2.2. Secondary Efficacy Analyses

Secondary endpoints AUC_{0(0.25-24)} and AUC_{0(0.25-72)} will be analyzed in same manner as the primary endpoint for the primary efficacy analysis set.

The secondary endpoints of percentage of opioid-free subjects through 24, 48 and 72 hours will be independently analyzed using a Chi-square test stratified on site for the primary efficacy analysis set. Treatment differences and 95% CIs will be derived using the normal approximation to the binomial.

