7.2. Current Therapies/Treatments

Current modalities of postoperative analgesia include infiltration with local anesthetic agents, and wound infiltration with local anesthetics combined with the systemic administration of analgesics (multimodal therapy). Multimodal therapy usually includes opioid medications, which have considerable drawbacks including time and resources required for monitoring opioid-related side effects. A reduction in the use of postoperative opioids is desirable to decrease the incidence and severity of opioid-induced adverse effects, such as respiratory depression, nausea, vomiting, constipation, somnolence, pruritus, and urinary retention.

There are almost 12 billion units of opioids prescribed in the US every year, almost 2 billion of which are from the oral surgery arena. Third molar extraction is associated with a defined period of pain and discomfort that often leads to the need for opioid analgesics. Unfortunately, this has the drawback of subjecting the patient to opioid-related adverse events (AEs); depending on the specific event, this can occur in up to 50% of patients ([Volkow 2011](#)). Previous studies with the use of EXPAREL have shown significant reduction in pain as well as total opioid consumption following both hard and soft tissue surgical procedures, along with a significant increase in many studies in median time to first opioid use. This delay was also associated with fewer opioid related adverse effects.

With over 70 million surgeries performed annually in the US, postoperative pain is a ubiquitous condition among our population. While it is a predictable component of the postoperative process, such pain is often poorly managed, resulting in clinical and physiological changes that increase morbidity and mortality (inability to ambulate early, etc.), diminish quality of life, and extend length of stay, thereby increasing hospital expenditures ([Oderda 2007](#)) and reducing patient satisfaction. Effective relief of acute pain with minimal opioid complications, on the other hand, may improve clinical outcomes, avoid complications (like delay in regaining bowel function or an inability to tolerate liquid and solid oral intake, etc.), and conserve healthcare resources. As such, the Joint Commission on Accreditation of Healthcare Organizations requires that all healthcare facilities practice adequate pain management and monitor opioid-related AEs ([Apfelbaum 2003](#)).

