15.3. Determination of Sample Size

In previous wound infiltrations studies in hemorrhoidectomy and bunionectomy, the difference between treatment groups in mean AUC from 0 to 48 hours or NRS pain intensity scores varied from 20 to 103. The standard deviations varied from 100 to 128. A sample size of 50 in each group will have 90% power to detect a difference in means of 66 assuming that the common standard deviation is 100 using a two group t-test with a 0.05 two-sided significance level. A sample size of 50 in each group will have 90% power to detect a difference in means of 86 assuming that the common standard deviation is 130 using a two group t-test with a 0.05 two-sided significance level.

However, the EXPAREL group will randomize approximately 100 subjects to lower the AE detection threshold for the safety database to 3%. The sample size for placebo was increased due to the additional collection of NRS pain intensity score immediately prior to all requests for rescue medication through 96 hours. The placebo sample size was increased to ensure that there are at least 50 subjects treated in both the EXPAREL and placebo under the current protocol amendment. It is expected that the sample size will be approximately 175 subjects resulting in a 2:1 ratio of EXPAREL to placebo subjects.

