15.6.3.2 Secondary Efficacy Measures

The secondary efficacy measures will be analyzed using a hierarchical fixed-sequence stepwise testing procedure. To protect the Type 1 error rate, the testing will be performed in a sequentially rejective fashion. If the first test is significant at the 0.05 level, then, and only then, the next secondary efficacy measure will be tested, and so forth. The results will be declared statistically significant at the 0.05 significance level.

Continuous Measures of Efficacy

For the AUC of pain intensity scores, missing data will be imputed as described in [Section 15.5](#) and fully described in the SAP.

For the integrated rank assessment that uses total amount of postsurgical opioids consumed through 48 hours, opioid medications will be converted to an IV morphine equivalent amount. All opioids consumed through 48 hours will be included in the analysis.

Summary statistics for each measure will be shown at each timepoint by treatment group. To test for significant differences between EXPAREL and placebo with respect to continuous measures of efficacy, an ANOVA with treatment as the main effect will be used. Based on the model, EXPAREL will be compared to placebo and two-sided CIs about the difference will be presented.

Categorical Measures of Efficacy

For categorizing subjects as pain-free, the NRS pain intensity score must be 0 or 1 at the assessed timepoint.

The proportion of subjects in each category will be calculated and summarized at each timepoint by treatment group. A chi-square test or Wilcoxon Rank Sum test will be used to compare EXPAREL to placebo.

Time to Event Measures of Efficacy

The time from start of study drug administration to the first use of an opioid rescue medication through 96 hours will be summarized with Kaplan-Meier estimates. A log-rank test will be used to compare EXPAREL to placebo.

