15.7. Significance Testing

All tests will be two-sided and based on a significance level of 0.05.

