7.6.2.3. Tertiary Efficacy Analyses

Tertiary endpoints will be summarized as appropriate (eg, descriptive statistics or tabulations). No statistical tests will be performed on these endpoints.

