7.6.2.3.12. Postsurgical Opioid Consumption (Rescue)

Postsurgical opioid consumption (MED) will be summarized (n, mean, SD, median, minimum and maximum) by treatment group for the total dose consumed over the 72 hours after the end of surgery. The number and percentages of the types of opioids used will be presented by treatment group. The number and percentage of subjects using any opioid will be presented by treatment for 24, 48 and 72 hours after dosing. This summary table will show summaries across all sites and for each site separately.

The number of times each subject used rescue medication thru 24, 48 and 72 hours will be tabulated across all sites and for each site separately.

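### The SAP drops the protocol's log-rank test of time to first opioid, leaving no pre-specified between-arm comparison of delay to rescue

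*SAP*

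**What the plan says.** Protocol 12.2 lists time to first opioid rescue as a tertiary endpoint. Protocol 15.6.3.2, under time-to-event measures, has it summarized by Kaplan-Meier from the start of study drug through 96 h and then says: "A log-rank test will be used to compare EXPAREL to placebo". The synopsis also names log-rank tests among the methods.

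The SAP keeps the endpoint (7.6.1.3) but not the test. Of the tertiary endpoints, 7.6.2.3 says: "No statistical tests will be performed on these endpoints". Sections 7.1.2 and 7.6 state the same rule. Section 7.6.2.3.7 gives Kaplan-Meier quartiles with 95% limits for each arm and a plot. The shell for Table 14.2-9 has no p-value, hazard ratio or between-arm interval.

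The opioid outcomes that are tested are the three opioid-free percentages, under SAP 7.6.2.2: "The secondary endpoints of percentage of opioid-free subjects through 24, 48 and 72 hours will be independently analyzed using a Chi-square test", stratified by site. They are the last three steps of the five-step fixed sequence in 7.1.2.

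**The concern.** The time of every rescue dose through 96 h is recorded, and the protocol said that the arms would be compared on time to the first one. Separate quartile intervals for each arm do not make that comparison, and a test added after unblinding would be post hoc by the SAP's own definition (section 2).

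The three opioid-free cuts do not fill the gap. A subject whose first dose moves from 4 h to 20 h is a user at 24, 48 and 72 h either way. If most subjects eventually take an opioid, a real delay can leave all three percentages nearly unchanged. Delay also belongs to the product's background case: Protocol 7.2 cites longer median time to first opioid in earlier studies.

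**Working it through.** **The plan's own power figure.** Protocol 15.3 gives, for 50 per group, "will have 90% power to detect a difference in means of 66 assuming that the common standard deviation is 100" and "will have 90% power to detect a difference in means of 86 assuming that the common standard deviation is 130". By normal approximation:
- 66/(100 × √(2/50)) − 1.96 = 3.30 − 1.96 = 1.34, power 91.0%.
- 86/(130 × √(2/50)) − 1.96 = 3.31 − 1.96 = 1.35, power 91.1%.

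The exact t-test gives 90.5% and 90.6%, so the stated 90% reproduces. It concerns the pain AUC. Neither document gives a power, a rate or a hazard ratio for any opioid endpoint.

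**Inputs for the illustration.** Protocol 15.7: "All tests will be two-sided and based on a significance level of 0.05". Sizes of 100 EXPAREL and 50 placebo follow SAP section 4 (at least 100 and 50) and the 2:1 ratio under Amendment 2. Assumed: proportional hazards with hazard ratio (HR) 0.6; placebo opioid-free at 24 h, p, from 2% to 30%; and a further 20% of the 24 h cumulative hazard accruing between 24 and 96 h. Site stratification is ignored.

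**One cell by hand, p = 10%.**
- EXPAREL opioid-free at 24 h: 0.10^0.6 = 0.251. Pooled proportion: (100 × 0.251 + 50 × 0.10)/150 = 0.201.
- 24 h chi-square: null SE = √(0.201 × 0.799 × (1/100 + 1/50)) = 0.0694. Alternative SE = √(0.251 × 0.749/100 + 0.10 × 0.90/50) = 0.0607. z = (0.151 − 1.96 × 0.0694)/0.0607 = 0.25, power about 60%.
- Log-rank: opioid-free at 96 h is 0.10^1.2 = 0.063 on placebo and 0.10^0.72 = 0.191 on EXPAREL. Events = 50 × 0.937 + 100 × 0.809 = 127.8. z = |ln 0.6| × √(127.8 × 2/9) − 1.96 = 2.72 − 1.96 = 0.76, power about 78%.

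**Full range, simulated under the same model (HR 0.6, 100:50).** The last column places log-rank as a sixth step behind the three opioid-free tests, with the primary and both AUC steps assumed to pass.

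| Placebo opioid-free at 24 h | Log-rank alone | 24 h opioid-free | Difference (points) | Log-rank as step 6 |
|---|---|---|---|---|
| 2% | 82% | 36% | 46 | 17% |
| 5% | 81% | 56% | 25 | 40% |
| 10% | 79% | 62% | 17 | 51% |
| 20% | 75% | 63% | 12 | 54% |
| 30% | 68% | 60% | 8 | 50% |

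**Other assumptions.**
- Smaller set, 67:33, p = 10%, HR 0.6: 62% for log-rank against 42% for the 24 h test.
- Delay only (median 8 h against 4 h among users, the same 5% to 10% never using in both arms), 100:50: log-rank 55% to 74%; opioid-free 31% to 44% at 24 h and 4% to 6% at 48 and 72 h.
- Never-users only (20% on EXPAREL against 5% on placebo, no delay among users): log-rank 61%; opioid-free 69% to 76%.

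**Definitions set side by side.** The clock starts at study drug administration in Protocol 15.6.3.2 and at end of surgery in SAP sections 5 and 7.6.1.9. The protocol's horizon is 96 h. SAP 7.6.2.3.7 counts ever/never users through 72 h but censors non-users at discharge or withdrawal, and discharge follows the 96 h assessments. SAP 7.6.1.9 also excludes subjects with missing pain scores, which this endpoint does not use.

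**The case against.** The strongest reply is that the dropped test was tertiary and outside the fixed sequence, so it could never have supported more than a nominal p-value. The SAP applies its no-test rule to all tertiary endpoints consistently, and the protocol defers detail to the SAP. Quartiles with intervals and a Kaplan-Meier plot will still be shown, and rescue use also enters the primary AUC through the worst-observation rule. All of that stands, and it limits the weight of the point. It does not explain why a comparison the protocol states outright was withdrawn.

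A reader might infer three stronger things that the documents do not support.

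- *That the opioid-free chi-square tests are themselves a mistake.* They are the protocol's own ordered secondary endpoints, tested by the protocol's own categorical method, and they can beat log-rank when the drug creates never-users.
- *That total opioid dose must be tested too.* SAP 7.6.2.3.12 says "Postsurgical opioid consumption (MED) will be summarized (n, mean, SD, median, minimum and maximum) by treatment group", and Protocol 7.2 says "Previous studies with the use of EXPAREL have shown significant reduction in pain as well as total opioid consumption". But that is product background. Total consumption is a stand-alone efficacy endpoint in neither document; in the protocol it enters only through the integrated rank assessment. Testing it is an optional new endpoint. Log-rank would not substitute for it: if only later doses fall by 40%, log-rank has 4% to 5% power, against 60% to 80% for a rank test on the number of doses.
- *That adding log-rank as step 6 turns the gain into controlled inference.* The last column of the table shows otherwise: 17% to 54%, below the existing 24 h test in every row.

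**Conclusion.** The point holds as an undeclared difference between protocol and SAP. The protocol plans a between-arm test of time to first opioid; the SAP provides none and, in the text available, gives no reason. Some SAP and addendum text was not available, so a reason could lie there.

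At HR 0.6 and 100:50, the forgone comparison would have 8 to 46 points more power than the 24 h opioid-free test, with the largest gap where few placebo subjects stay opioid-free. Those figures rest wholly on assumed rates, proportional hazards and an unstratified analysis, and the direction reverses if the drug acts mainly by creating never-users. The primary analysis, the five secondary tests and their type I error are unaffected. It does not follow that the trial cannot assess opioid sparing: the opioid-free tests remain, and the timing and dose data are reported descriptively.

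**What to change.** In SAP 7.6.2.3 and 7.6.2.3.7, restore the log-rank test of time to first opioid rescue through 96 h, stratified by site to match 7.6.2.2, with a hazard ratio and 95% CI. State that it is a tertiary analysis outside the fixed sequence and that its p-value is nominal. Amend the no-test statements in 7.1.2 and 7.6 to allow this exception, and add the results to Table 14.2-9. Leave the five gated secondary endpoints as they are. If the sponsor prefers not to test, the SAP should declare the departure from the protocol and give the reason.

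In the same edit, choose one time origin and one horizon for this endpoint in both documents, and remove the missing-pain-score exclusion from 7.6.1.9.

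The cost is a few lines of text and a few table rows, with no new data and no alpha taken from the primary or secondary tests. The downside is one more uncontrolled p-value. The change should be made before unblinding; after that the test would be post hoc and should be labelled so.

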7.6.2.3. Tertiary Efficacy Analyses

Tertiary endpoints will be summarized as appropriate (eg, descriptive statistics or tabulations). No statistical tests will be performed on these endpoints.

7.6.2.3.1. AUC(0.25-96)

The NRS AUC(0.25-96) will be summarized (n, mean, SD, median, minimum and maximum) by treatment group. The summary will be based on the data obtained using multiple imputations.

7.6.2.3.2. SPI(0.25-24), SPI(0.25-48), SPI(0.25-72) and SPI(0.25-96)

The NRS SPI(0.25-24), SPI(0.25-48), SPI(0.25-72) and SPI(0.25-96) will be summarized (n, mean, SD, median, minimum and maximum) by treatment group. The summary will be based on the data obtained using multiple imputations.

7.6.2.3.3. Numeric Rating Scale Pain Intensity Scores by Assessment Timepoint

The NRS pain intensity scores will be summarized (n, mean, SD, median, minimum and maximum) at each scheduled assessment timepoint for each treatment group. The summaries and figures will be based on the data obtained using multiple imputations.

The NRS pain intensity scores will also be summarized (n, mean, SD, median, minimum and maximum) prior to each rescue medication. The summary will also include the median, minimum and maximum time to rescue for those subjects using rescue medication. Rescue medication will be presented in order of the request for rescue medication, e.g., first request, second request and so on. The time to request for rescue medication may differ widely from subject to subject. Only subject with NRS pain scores prior to rescue will be presented in this summary.

Plots of NRS pain intensity scores over time from baseline to last assessment will be presented for the mean (\pm SD) and individual subjects. The mean plot will be presented for both the observed and imputed mean values. The mean plot will be based only on the scheduled NRS assessment scores. The subject plots will be show both the scheduled and immediately prior to rescue NRS assessment scores. On the subject plots, scores obtained prior to rescue medication use will be differentiated from the scheduled scores. The subject plots will present the observed and imputed scores separately. The scores will be connected using straightlines.

7.6.2.3.4. Numeric Rating Scale Pain Intensity Scores Partial Area Under the Curve

The NRS AUC(24-48) and AUC(48-72) will be summarized (n, mean, SD, median, minimum and maximum) by treatment group. The summary will be based on the data obtained using multiple imputations.

7.6.2.3.5. Percentage of Pain-free Subjects by Assessment Timepoint

The number and percentage of subjects ever and never using opioids from end of surgery through each NRS assessment timepoint will be tabulated by treatment. Missing NRS values will not be imputed for this summary. Subjects will be excluded from the summaries where they are missing NRS values.

A bar chart presenting the percentage of pain-free subjects at each assessment timepoint will be provided.

7.6.2.3.6. Percentage of Opioid-free Subjects Through 96 hours

The number and percentage of subjects ever and never using opioids from end of surgery through 96 hours will be tabulated by treatment.

A bar chart presenting the percentage of opioid-free subjects at 24, 48 and 96 hours will be provided.

7.6.2.3.7. Time to First Opioid Rescue Medication

The number and percentage of subjects ever and never using opioids after surgery through 72 hours will be presented by treatment. Subjects who did not take opioids will be censored at the time of discharge from the clinic or from the time of withdrawal, whichever is sooner. The 25th (first quartile), 50th (median – second quartile) and 75th (third quartile) percentiles, minimum and maximum time to first use of opioid rescue medication will be estimated using Kaplan-Meier methods. The quartile and the 95% confidence limits for each quartile will be presented by treatment. This summary will be presented overall and for each site.

A Kaplan-Meier plot of the time to first rescue medication use will be presented.

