13.7. Day 10 Visit

- Collect scheduled blood sample for PK analysis.
- Perform neurological assessment (see [Appendix 4](#)).
- Conduct 12-lead ECG.
- Document any unscheduled phone calls or office visits related to pain since Day 7.
- Obtain overall rating of subject satisfaction with postsurgical pain control using the Likert scale (see [Appendix 2](#)).
- Record concomitant medications including opioid rescue.
- Record AEs and any treatment(s) for the events.

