7.1.1.3. Surgery Date or Time

It is expected that all necessary information on surgery (start and stop date and time) and postsurgical rescue medication (start dates and times, doses, frequency) will be complete. Any such information that is missing and cannot be obtained through query resolution may be imputed, on a case-by-case basis, in a conservative manner that minimizes bias. For example, if pain medication taken on Day 1 has no time of administration recorded, the imputed time will be the end of surgery.

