7.1.1.7. Time to Event

For calculating time to an event when only the hour is reported, the minutes will be set to zero. If only date is reported, the time will be set to midnight (00:00).

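### SAP 7.6.2.3.7 uses inconsistent horizons for time to first opioid: 72 h for the count, discharge for censoring, and none for events

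*SAP*

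**What the plan says.** Time to first opioid rescue is a tertiary endpoint. Protocol 15.6.3.2 gives it a fixed end: "The time from start of study drug administration to the first use of an opioid rescue medication through 96 hours" is to be summarised by Kaplan-Meier. Protocol 12.1 also lists opioid rescue as an efficacy measurement through 96 h.

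SAP 7.6.2.3.7 does not restate that end.

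- **Count:** "The number and percentage of subjects ever and never using opioids after surgery through 72 hours will be presented by treatment".
- **Censoring:** "Subjects who did not take opioids will be censored at the time of discharge from the clinic or from the time of withdrawal" (the earlier of the two). Under Protocol 13.5, discharge follows the 96-hour assessments. SAP Section 5 accepts elapsed times of 0 to 100 h for the 0-96 h frame.
- **Events:** no upper limit. SAP 7.6.1.9 defines only the interval from end of surgery to the event.
- **Table 14.2-9:** the shell splits subjects into rescued and not rescued, labels the second row as censored, and states no horizon. The SAP addendum reuses this shell for the per-protocol set (Table 14.2-9.1).

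Opioid use after discharge will be in the database. Protocol 11.6.3 requires analgesics to be documented through Day 10, and Protocol 13.6 and 13.7 both carry the instruction "Record concomitant medications including opioid rescue". SAP Section 4 still describes opioid documentation through 96 h only.

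For missing times, SAP 7.1.1.3 gives this example: "if pain medication taken on Day 1 has no time of administration recorded, the imputed time will be the end of surgery". SAP 7.1.1.7 sets any time-to-event date without a clock time to midnight.

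**The concern.** One summary should follow one period. Here a subject first rescued at 80 h belongs with the never-users in the 72 h count and with the events in the curve.

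The missing event limit is a separate problem. Read literally, a subject whose first opioid is taken at home on Day 6 did take opioids and becomes an event at about 120 h, while every subject who never took one left the risk set at discharge. Whether a subject stays at risk after discharge then depends on what happens later, which Kaplan-Meier does not allow. The upper quartiles, their confidence limits, the maximum and the plotted tail could then reflect prescribing after 96 h, when the regimen may be adjusted, instead of the supervised period. If late uses fell in only one arm, that arm's curve would drop to zero while the other stayed flat.

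**Working it through.** The plan states no figure for this endpoint, so there is none to reproduce. The check compares the rules with each other and then applies the product-limit formula to illustrative data. All counts below are assumptions: 100 subjects in an arm; discharge at 97 h; 5 first uses evenly spaced from 73 to 95 h; F subjects opioid-free at 96 h (10, 20, 30, 40 or 60); and L of those F with a first use after discharge (1, 3 or 5), placed between 110 and 150 h, or at 130 h when L = 1.

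**Step 1: count against curve.** Take F = 40. Never-users through 72 h = 40 + 5 = 45. Event-free at discharge = 40. The two differ by 5, the number first rescued between 72 h and discharge. If the SAP's 0 to 76 h window for the 0-72 h frame is applied to the count, the use at 73 h moves across and the comparison is 44 against 40. This step needs no post-discharge use.

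**Step 2: tail of the curve.** After discharge the risk set holds only the L late users. Survival after the j-th late use is S = (F/100) × (1 − j/L), which is zero at j = L whatever F is.

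- F = 30, L = 5: S = 0.30 × (4/5, 3/5, 2/5, 1/5, 0) = 0.24, 0.18, 0.12, 0.06, 0. The third quartile is the first late use, at 110 h.
- F = 40, L = 3: S = 0.40 × (2/3, 1/3, 0) = 0.267, 0.133, 0. The third quartile is the second late use, at 130 h, and 37 subjects are censored. If follow-up stops at discharge, S ends at 0.40, the third quartile is not estimable (NE) and 40 are censored.

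**Step 3: range.** Ranges cover L = 1, 3 and 5.

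| F | Final S, late uses counted | Final S, stopped at discharge | Third quartile, counted / stopped | Median, counted / stopped |
|---|---|---|---|---|
| 10 | 0.00 | 0.10 | no change | no change |
| 20 | 0.00 | 0.20 | no change | no change |
| 30 | 0.00 | 0.30 | 110-130 h / NE | no change |
| 40 | 0.00 | 0.40 | 120-130 h / NE | no change |
| 60 | 0.00 | 0.60 | 130 h / NE | 110-130 h / NE |

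The third quartile moves only if survival at discharge exceeds 0.25, and the median only if it exceeds 0.50. If no late use is counted, nothing in Steps 2 and 3 changes.

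**Step 4: Day 1 rescue without a time.** Suppose surgery ends at 11:00. Section 7.1.1.3 gives 0 h. Section 7.1.1.7 gives 00:00 − 11:00 = −11 h, an impossible time for a postsurgical event.

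**The case against.** The strongest reply is that the protocol already closes the gap. It limits the endpoint to first use through 96 h, its efficacy measurement of rescue stops at 96 h, and SAP Section 2 sends readers to the protocol. On that reading a take-home dose is never an event and the tail is sound. Much of this stands: the SAP omits a clause; it does not specify a wrong analysis. But the protocol labels post-discharge use as opioid rescue in the Day 7 and Day 10 records, and a programmer following 7.6.1.9 and 7.6.2.3.7 alone finds no limit.

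On the count, SAP 7.6.2.3.6 already tabulates ever and never use through 96 h, and the rows of Table 14.2-9 could be filled from the Kaplan-Meier status. That limits the damage, but the text of 7.6.2.3.7 still says 72 h.

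On an untimed Day 1 rescue, 7.1.1.3 is the more specific rule and expects such data to be complete. A careful reader would choose it, but the SAP does not say that it takes precedence.

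A reader might infer three stronger things, none of which the documents support.

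- **Censoring at discharge is itself an error.** It is not. Discharge follows the 96-hour assessments, and the SAP's 0-96 h frame runs to 100 h.
- **The tail and quartiles are wrong as planned.** They can be wrong, but only if a post-discharge first use is counted, and quartiles move only above the thresholds in Step 3.
- **The midnight rule moves date-only withdrawals up to 24 h early.** Section 7.1.1.7 names neither withdrawal nor censoring. The shell of Listing 16.2-1 shows a date without a time, but an output shell does not show what the CRF records. Even if the rule were applied, moving 1 to 5 withdrawals per 100 earlier by 15 h changed final survival by 0.001 to 0.005 and the median by 0 to 1.3 h in illustrative runs.

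**Conclusion.** The inconsistency is real and visible in the text. Section 7.6.2.3.7 applies 72 h to the count, discharge to censoring and no limit to events, against the protocol's 96 h. The count mismatch equals the number first rescued between 72 h (or 76 h with the window) and discharge, and it needs only one such subject. The tail problem is conditional: a first use after the last discharge must occur and be counted as an event. The curve then ends at zero, against 0.10 to 0.60 in the illustrations. The true share opioid-free at discharge and the number of late users are not given in the documents, so the sizes shown are ranges under assumptions, not forecasts.

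The consequence is limited. SAP 7.6.2.3 plans no test of tertiary endpoints, and Table 14.2-9 is not among the topline tables. The descriptive quartiles and the plot are what is at risk.

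**What to change.** In SAP 7.6.2.3.7, use one horizon throughout. Suggested wording:

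*Time to first opioid rescue is analysed over the 0-96 h period, with accepted elapsed times to 100 h, or to discharge, whichever is first. A first opioid dose within that period is an event. A subject with none is censored at the end of that period, or at withdrawal if earlier. Ever and never users are presented for the same period.*

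This replaces 72 h with 96 h in the count, so that never-users match the censored row of Table 14.2-9 and of its per-protocol copy. Refer 7.6.2.3.6 to the same definition. Avoid a hard cut at 96 h: an in-clinic first rescue at 98 h lies inside the SAP's 0-96 h window and would otherwise be ever-use in one table and censored in another.

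In 7.1.1.7, add that a Day 1 rescue without a recorded time takes the end of surgery under 7.1.1.3, not midnight.

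The cost is a few sentences of SAP text and minor programming. No new data are needed.
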